11.4.1. Group assignment under the “as-treated” principle

- **Endovascular therapy:** Patients who present to the endovascular suite (cath lab) and undergo a femoral puncture within 24 hours after time of onset of the qualifying stroke are assigned to the endovascular treatment arm under the “as-treated” principle.
- **Medical therapy:** Patients who do not meet the above criteria for endovascular treatment are assigned to the medical treatment arm under the “as-treated” principle.

12. Analyses of secondary efficacy outcomes

12.1. Analyses of secondary clinical efficacy outcome: functional independence

The effect of endovascular treatment will be assessed on a secondary clinical efficacy outcome: functional independence at 90 days, defined as an mRS score ≤ 2 at day 90. Results will be expressed as an unadjusted risk ratio with its 95% confidence interval and p-value.

12.2. Analyses of functional independence in subgroups

The unadjusted effect of endovascular treatment on the secondary efficacy outcome “functional independence” (mRS ≤ 2) will be analyzed in the following subgroups, assuming sufficient numbers of subjects are enrolled in each subgroup (minimum required is 10% of the total sample size in each subgroup). Results will be expressed as unadjusted risk ratios with their 95% confidence intervals and p-values. We will assess for differences in the treatment effect between subgroups (eg, age <70 vs ≥ 70) using a Breslow-Day test for binary covariates, or by including an interaction term into a logistic regression model for covariates with greater than 2 categories.

- Time from symptom onset to randomization (using the categories from the dynamic stratification: <9 , 9-12, >12 hr ~~endpoint from adaptive design~~)

- Baseline ischemic core lesion volume based on Central Lab reading (~~using cutpoints from adaptive design~~ using the three categories from the dynamic stratification: <10.0, 10.0-25.0, > 25.0 mL)
- Age at randomization (<70 and \geq 70 years old)
- Baseline NIHSSS using the categories from the dynamic randomization (<13, 13 - 18 and >18)
- Baseline ASPECTS based on Central Lab reading (<8 and \geq 8)
- Primary occlusion site based on Central Lab reading (M1 and ICA)
- IV rt-PA treatment (yes and no)
- Patient selection (CTP versus MRI)
- ~~Collateral grade (0-1, 2, 3)~~
- Method by which symptom onset time was determined (last known well vs exact time of symptom onset)
- Sex
- Race (White, Non-white)
- Ethnicity (Hispanic and Non-Hispanic)
- Baseline atrial fibrillation (yes and no)

12.3. Analyses of imaging efficacy outcomes

We hypothesize that endovascular treatment improves radiological outcomes. We will compare four imaging outcomes between treatment groups:

- The proportions of successful reperfusion, where successful reperfusion is defined as a >90% reduction in the volume of brain tissue with critical hypoperfusion ($T_{max} > 6$ sec after artifact removal by core lab) between baseline and 24 hours. Results will be expressed as an unadjusted risk ratio with its 95% confidence interval and p-value.
- The proportion of subjects with recanalization of the primary arterial occlusive lesion (ICA or M1) at the time of the 24-hour follow-up scan is compared between the two treatment arms. Results will be expressed as an unadjusted risk ratio with its 95% confidence interval and p-value.
- Infarct volumes at 24 hours, defined as the lesion volume as outlined on the 24-hour DWI (or CT if DWI not performed). The 24-hour endpoint is based on data demonstrating that assessment of infarct volume at 24 hours captures the effect of reperfusion therapies on infarct growth and predicts outcomes similarly to day 90 infarct volumes.^{8, 9} The Wilcoxon rank-sum will be used to compare the treatment groups.
- Ischemic lesion growth between baseline and 24 hours defined as the difference between the baseline ischemic core lesion volume and the 24-hour DWI lesion volume (or CT if DWI not performed). Absolute lesion growth will be calculated by subtracting the baseline ischemic core lesion volume from the 24-hour DWI lesion volume. DEFUSE 2 demonstrated a substantial reduction in infarct growth among Target mismatch patients treated in the 6-12 hour time-window who achieved early reperfusion: median growth 0.5 ml (IQR: -2 – 10) with reperfusion (n=23) vs. 39 ml (IQR: 18-121) without reperfusion (n=13), $p < 0.001$. The Wilcoxon rank-sum will be used to compare the treatment groups.

We also hypothesize that final infarct volumes (assessed on 24-hour DWI) can be predicted based on baseline ischemic core and critically hypoperfused tissue volumes. To analyze this relationship, subjects will be divided into two groups: 1) patients with reperfusion, defined as >90% reduction in the $T_{max} > 6$ -second lesion volume between baseline and 24 hours (or TIC1 2b–3 at end of procedure if perfusion imaging inadequate) and (2) a “no reperfusion” group, defined as <10% reperfusion at 24 hours. Spearman’s rho will be used

to assess correlations between: 1) baseline ischemic core volume and 24-hour DWI lesion volume in patients with reperfusion; and 2) the union of baseline ischemic core volume and 24-hour critically hypoperfused lesion volume (Tmax6) and 24-hour DWI lesion volume in patients without reperfusion.

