1. ICA or MCA-M1 occlusion (carotid occlusions can be cervical or intracranial; with or without tandem MCA lesions) by MRA or CTA

AND

2. Target Mismatch Profile on CT perfusion or MRI (ischemic core volume is < 70 ml, mismatch ratio is ≥ 1.8 and mismatch volume* is ≥ 15 ml)

Notes: The mismatch volume is determined by the RAPID software in real time based on the difference between the ischemic core lesion volume and the $T_{max}>6s$ lesion volume. If both a CT perfusion and a multimodal MRI scan are performed prior to enrollment, the later of the 2 scans is assessed to determine eligibility. Only an intracranial MRA is required for patients screened with MRA; cervical MRA is not required. Cervical and intracranial CTA are typically obtained simultaneously in patients screened with CTA, but only the intracranial CTA is required for enrollment.

Alternative neuroimaging inclusion criteria (if perfusion imaging or CTA/MRA is technically inadequate):

- A) If CTA (or MRA) is technically inadequate:

$T_{max}>6s$ perfusion deficit consistent with an ICA or MCA-M1 occlusion

AND

Target Mismatch Profile (ischemic core volume is < 70 ml, mismatch ratio is ≥ 1.8 and mismatch volume is ≥ 15 ml as determined by RAPID software)

- B) If MRP is technically inadequate:

ICA or MCA-M1 occlusion (carotid occlusions can be cervical or intracranial; with or without tandem MCA lesions) by MRA (or CTA, if MRA is technically inadequate and a CTA was performed within 60 minutes prior to the MRI)

AND

DWI lesion volume < 25 ml

- C) If CTP is technically inadequate:

Patient can be screened with MRI and randomized if neuroimaging criteria are met.

3.3.4. Neuroimaging Exclusion Criteria:

1. ASPECT score < 6 on non-contrast CT (if patient is enrolled based on CT perfusion criteria)
2. Evidence of intracranial tumor (except small meningioma) acute intracranial hemorrhage, neoplasm, or arteriovenous malformation
3. Significant mass effect with midline shift
4. Evidence of internal carotid artery dissection that is flow limiting or aortic dissection
5. Intracranial stent implanted in the same vascular territory that precludes the safe deployment/removal of the neurothrombectomy device
6. Acute symptomatic arterial occlusions in more than one vascular territory confirmed on CTA/MRA (e.g., bilateral MCA occlusions, or an MCA and a basilar artery occlusion).

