Imaging outcomes: We hypothesize that endovascular treatment improves radiological outcomes in stroke patients with favorable clinical and imaging characteristics. DEFUSE 2 demonstrated a substantial reduction in infarct growth among Target mismatch patients treated in the 6-12 hour time-window who achieved early reperfusion: median growth 0.5 ml (IQR: -2 – 10) with reperfusion (n=23) vs. 39 ml (IQR: 18-121) without reperfusion (n=13), p<0.001. These data have been extrapolated to DEFUSE 3 using the same assumptions described above; anticipated an early reperfusion rate of 75% in the endovascular arm vs. 20% in the medical arm. This yields a sample size of 42 per group for 90% power. Therefore, DEFUSE 3 is highly powered to demonstrate differences in lesion growth. Infarct volumes, ischemic lesion growth, and reperfusion rates at 24 hours will be compared between groups with the Mann-Whitney U test. The 24 hour endpoint is based on data demonstrating that assessment of infarct volume at 24 hours captures the effect of reperfusion therapies on infarct growth and predicts outcomes similarly to day 90 infarct volumes.^{29, 62} RAPID-assessed ischemic core volume at baseline will be correlated with 24h infarct volume (DWI volume) in subjects who achieve reperfusion without PH1 or PH2 intracranial hemorrhage. Pearson's correlation coefficient will be calculated and the median absolute error (ml) will be reported. Similarly, correlation of the baseline Tmax >6 volume and the 24h infarct volume in patients without PH1 or PH2 intracranial hemorrhage who have <10% reperfusion will be performed. Correlation of RAPID predicted infarct volume (coregistered baseline ischemic core and 24h Tmax >6 volume) with the actual 24h infarct volume will also be performed.

Scenario	Standardized effect in cells							Average standard effect	Adaptive Design		Fixed Design	
	C11	C12	C21	C22	C31	C32	Average No. randomized		Power	Number randomized	Power	
#0	0	0	0	0	0	0	0	361	2.2%	476	2.5%	
#1	0.3	0.3	0.3	0.3	0.3	0.3	0.3	354	80%	476	89%	
#2	0.5	0.4	0.3	0	0	0	0.2	400	86%	476	55%	
#3	0.5	0.5	0	0	0	0	0.17	403	87%	476	41%	

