5.3. Safety sample

The safety sample includes all randomized subjects. Thus, the safety sample is the same, regardless of whether a subgroup is selected to continue enrollment ~~by the adaptive design.~~ See Section 13 for details of the safety analyses.

6. Randomization

Randomization takes place centrally via the DEFUSE 3 Trial WebDCU™ website. The randomization scheme is the combination of minimization and the biased coin method and is never deterministic. A dynamic stratification system will ensure well-balanced subgroups. The randomization algorithm will employ biased-coin minimization and the variance method with stratification weights.¹ The strategy is to balance treatment assignment along the marginal distribution of each stratification factor. The stratification factors used and their hierarchy will be: 1) ischemic core volume, 2) age, 3) time from symptom onset to enrollment, 4) NIHSS score and 5) study site. When a new patient is enrolled, the site will enter the stratification factor values into the eCRF (electronic case report form) on WebDCU™. The dynamic randomization

algorithm will determine an imbalance measure for each treatment group. The treatment group associated with the smallest imbalance measure will receive the largest probability of assignment in the biased-coin randomization. The randomization algorithm will be programmed into the WebDCU™ and validated using test samples by the NDMC. The detailed randomization scheme, including biased coin acceptance region and stratification weights, and source codes are provided in the Randomization Plan document. (Appendix 1)

7. Blinding

The acute treatment phase of the study is conducted in an open-label manner. However, study investigators who are not directly involved with acute treatment of the subject and who are blinded to treatment assignment will conduct all 30 and 90-day outcome assessments. To maintain blinding of the assessor, subjects are instructed not to discuss their initial hospitalization and treatment with the assessor.

In cases where an unblinded assessor performed the 30- or 90-day assessment (the CRF will capture if the assessor was blinded; this variable will be self-reported by the assessor), such occurrence will be marked as a protocol violation and presented in the final study report; nevertheless, the submitted data are used in the analysis.

8. Handling of Missing Data at the Final Analysis

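### The 24-hour infarct volume test in SAP 12.3 leaves out baseline core volume, a randomization factor that is already collected, at a modest cost in precision

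*SAP*

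**What the plan says.** SAP 12.3 defines the outcome as "Infarct volumes at 24 hours, defined as the lesion volume as outlined on the 24-hour DWI (or CT if DWI not performed", and the test as "The Wilcoxon rank-sum will be used to compare the treatment groups". Protocol 3.8 agrees: "Infarct volumes, ischemic lesion growth, and reperfusion rates at 24 hours will be compared between groups with the Mann-Whitney U test". The two documents do not conflict, and neither names a covariate or stratum.

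The next outcome in SAP 12.3 does use baseline: "Absolute lesion growth will be calculated by subtracting the baseline ischemic core lesion volume from the 24-hour DWI lesion volume". It is tested in the same way.

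Baseline core is available for essentially everyone randomized. Protocol 3.3.3 requires "ischemic core volume is < 70 ml, mismatch ratio is ≥ 1.8 and mismatch volume" above a limit; where MR perfusion is inadequate, it requires a DWI lesion volume below 25 ml instead. SAP section 6 lists the randomization factors as "1) ischemic core volume, 2) age, 3) time from symptom onset to enrollment, 4) NIHSS score and 5) study site". SAP 12.2 already carries Central Lab core as an analysis variable, "using the three categories from the dynamic stratification: <10.0, 10.0-25.0, > 25.0 mL".

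The covariate-adjusted analyses in SAP 11.3 include core volume but concern only the 90-day mRS.

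**The concern.** The 24-hour lesion largely contains the baseline core, so part of its spread between patients is fixed before treatment. Protocol 2.2 says that in DEFUSE 2 the early DWI lesion forecast the final infarct dependably in fully reperfused patients, and SAP 12.3 itself hypothesizes that final infarct can be predicted from baseline core and hypoperfused volumes. An unadjusted rank test counts this predictable spread as noise.

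It also ignores the fact that randomization balances the arms on core. When arms are balanced on a prognostic factor and the test ignores it, the test is conservative. At stake are the power of one imaging comparison and the precision of what is reported for it.

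**Working it through.** **Inputs from the documents.** Baseline core in DEFUSE 2 Target Mismatch patients: median 13 ml, IQR 5-26 (protocol 2.1). Growth: median 0.5 ml (IQR -2 to 10) with reperfusion and 39 ml (IQR 18-121) without; reperfusion 75% versus 20% (protocol 3.8). Core limit 70 ml (protocol 3.3.3). 182 randomized when a halt to enrollment was requested (SAP section 2), so about 91 per arm at 1:1.

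**Assumptions.** Two-sided 5%, which SAP section 10 states for the primary endpoint and nothing states for imaging. Core-growth correlation of 0, 0.3 or 0.5. Distribution shapes, since only quartiles are given.

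**1. The plan's own figure.** Protocol 3.8 gives 42 per group for 90% power on growth. With each arm a mixture of the two growth distributions, Noether's formula per arm is n = (1.960 + 1.282)² / [6(P - 0.5)²] = 10.51 / [6(P - 0.5)²].

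- Shifted lognormal through the quartiles: P = 0.716, so 10.51 / (6 × 0.0467) ≈ 38.
- Split normal: P = 0.695, so 10.51 / (6 × 0.0380) ≈ 46.

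The stated 42 lies between the two and is plausible. No sample size is given for 24-hour volume. At 42 per arm the unadjusted volume test has simulated power of 72-83%, against 87-95% with rank ANCOVA, so 90% at that size does not carry over from growth to volume.

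**2. Efficiency.** Core (lognormal, truncated at 70 ml) plus growth gives a within-arm rank correlation ρ between core and 24-hour volume of about 0.40 to 0.66. Adjustment multiplies the variance by 1 - ρ²:

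- ρ = 0.40: 1 - 0.16 = 0.84; 1/0.84 = 1.19, a gain of 19%.
- ρ = 0.664: 1 - 0.441 = 0.559; 1/0.559 = 1.79, a gain of 79%.

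A second simulation added baseline measurement error (CV 0 to 0.7, assumed) and measured the gain as (adjusted Z / unadjusted Z)² - 1. It gave 12-19% at correlation 0, 27-43% at 0.3 and 42-72% at 0.5. Together the range is about 12-79%.

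**3. Power at 91 per arm, %.** The 75% versus 40% contrast is an assumption and is not in the documents.

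| Shape, core-growth correlation | Reperfusion | Volume, Wilcoxon | Volume, van Elteren | Volume, rank ANCOVA | Growth, Wilcoxon (planned) |
|---|---|---|---|---|---|
| Lognormal, 0 | 75 v 20 | 99.0 | 99.8 | 99.6 | 100 |
| Lognormal, 0.3 | 75 v 20 | 98.6 | 100 | 99.7 | 100 |
| Lognormal, 0.5 | 75 v 20 | 98.8 | 100 | 100 | 100 |
| Split normal, 0 | 75 v 20 | 99.1 | 99.4 | 99.7 | 99.8 |
| Split normal, 0.3 | 75 v 20 | 96.7 | 99.4 | 99.5 | 99.6 |
| Split normal, 0.5 | 75 v 20 | 96.2 | 99.6 | 99.9 | 99.7 |
| Lognormal, 0 | 75 v 40 | 75.8 | 87.2 | 83.6 | 90.1 |
| Lognormal, 0.3 | 75 v 40 | 74.3 | 88.8 | 88.5 | 91.0 |
| Lognormal, 0.5 | 75 v 40 | 74.5 | 92.3 | 93.1 | 92.5 |
| Split normal, 0 | 75 v 40 | 75.8 | 81.1 | 84.8 | 83.4 |
| Split normal, 0.3 | 75 v 40 | 67.9 | 79.8 | 84.5 | 81.7 |
| Split normal, 0.5 | 75 v 40 | 66.3 | 82.8 | 88.5 | 83.2 |

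Rank ANCOVA gains 0.6 to 3.7 points over the unadjusted test at 75 versus 20, and 7.8 to 22.2 points at 75 versus 40. Against the planned growth test its difference runs from -0.4 to +0.2 points at the planned contrast, and from -6.5 to +5.3 points at the smaller one.

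**4. Size.** Under the null, with patients paired within core categories, the unadjusted test rejects in 1.7-3.8% of trials at nominal 5%, and rank ANCOVA in 4.3-5.3%. Pairing balances core more tightly than biased-coin minimization is likely to, so take the direction rather than the exact figures.

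**The case against.** The strongest reply is that baseline core is already used where it matters. Lesion growth is the imaging outcome that the protocol sized, it subtracts core, and its planned test does about as well as the proposed adjustment. SAP 3.1 treats imaging as supportive. An unadjusted analysis is also the plan's consistent choice for the primary, secondary and subgroup effects. The larger efficiency figures need correlations of 0.3 or 0.5 that the documents do not supply, and the 8-22 point loss needs a reperfusion contrast that they do not contain.

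All of this stands, and it limits the point to a refinement. It does not remove it: 24-hour volume is listed separately, with its own test, and the SAP already accepts Central Lab core as a covariate for the mRS.

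A reader might go further and infer that the growth comparison is harmed because it can subtract a CT-perfusion core from a 24-hour DWI outline. The documents do not support that. Baseline modality is fixed before randomization, so it gives no reason to expect bias between arms. Protocol 2.2 says that CT perfusion processed with the same software identifies core about as accurately as MRI. In the simulation with baseline error, adjusting growth for core changed efficiency by only -1% to 12%. A modality main effect would shift the intercept and would not correct a difference in scale.

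**Conclusion.** The point holds as a low-priority improvement. The test of 24-hour infarct volume ignores a prognostic randomization factor that is already measured. Adjustment is worth roughly 12-79% in efficiency for that comparison, over assumed core-growth correlations of 0 to 0.5 and assumed distribution shapes and measurement error. Under the plan's own reperfusion rates and 182 patients, this comes to about 1-4 points of power from a base of 96-99%, and the planned growth test recovers most of it.

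A reader might infer that the imaging comparison is invalid or underpowered. Neither follows: the unadjusted test errs on the conservative side, with no inflation of type I error, and its power is high under the planning assumptions.

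**What to change.** In SAP 12.3, make the 24-hour infarct volume test a rank ANCOVA on Central Lab baseline core volume, or a van Elteren test stratified by the three core categories used in randomization. Keep the unadjusted Wilcoxon as a sensitivity analysis. Leave the lesion-growth outcome and its test unchanged.

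Rank ANCOVA gives a test on ranks, not a difference in ml. If an adjusted difference with a 95% confidence interval is wanted, name the estimator, for example median regression or regression on a transformed volume.

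The cost is a few lines of SAP wording and a little programming; no new data are needed. Version 3.1 was still adding clarifications before the Stanford team was unblinded, so the change would have fitted there. If it is made after unblinding, label it post hoc.

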12.4. Additional pre-planned analyses

- Assessment of the effect of endovascular therapy on the following endpoints will be assessed: (1) >8 point improvement on the NIHSS between baseline and 24 hrs or an NIHSS score of 0-1 at 24 hrs; (2) discharge destination (home vs other); (3) number of days spent at home during first 90 days after stroke; and (4) mRS score at day 30 (both with an ordinal analysis and dichotomous at 0-2).
- Assessment of the interaction between time-to-treatment randomization and the effect of endovascular therapy (expressed as the common odds ratio for shift on the 90-day mRS)
- Assessment of imaging predictors of growth of the ischemic lesion between baseline and 24 hours stratified by treatment allocation and reperfusion status. Specific baseline imaging predictors that will be evaluated include the ratio of the Tmax 10 / Tmax 6 lesion volumes and the CBV value within the Tmax 6 lesion volume.

13. Safety analyses

All safety outcome measures are analyzed under the as-treated principle. Under this principle, each subject is analyzed according to the treatment that the subject received. The external Medical Safety Monitor and the DSMB will monitor safety variables throughout the study at frequent intervals. Details of this process are specified below.

13.1. Monitoring of deaths and sICH

The primary safety endpoints are deaths and sICH rates; these will be monitored quarterly. Symptomatic ICH or death rates that exceed pre-specified thresholds will trigger a meeting of the DSMB. The DEFUSE 3 study will be placed on hold if it is determined with 95% probability that either:

- 1) the symptomatic ICH rate (NIHSS worsening of 4 or more points associated with ICH) within 36 hours of randomization exceeds 10% in the endovascular group; OR
- 2) the 90-day mortality rate exceeds 20% in the endovascular group.

The study will remain on hold until the investigators and the DSMB can conduct a review of events and make a determination on the continuation of the trial.

13.2. Summary of Adverse Events (AEs) and Serious Adverse Events (SAEs)

All AEs and SAEs are summarized by MedDRA preferred term (as coded based on the AE CRF) and by treatment group in terms of frequency of the event, number of subjects having the event, timing relative to randomization, and relatedness to the intervention.

For the following specific events, the proportions by treatment group, as well as the RR and corresponding 95% confidence interval, are provided:

- Stroke related mortality within 90 days of randomization

- sICH within 36 hours of randomization
- Significant neurological deterioration prior to discharge (defined as an increase of 4 points or more on the NIHSS)
- PH1 and PH 2 rates on the 24 hr scan

At the end of the study, the cumulative incidences of these events are compared between the two treatment groups using Pearson Chi-Square. Fisher's exact test will be used if any cells are 5 or less.

All brain scans obtained prior to discharge will also be assessed for PH by the core lab.

14. Coordination between Stanford and MUSC statistical teams

The primary statistician for the study is Dr. [REDACTED] at Stanford. He is a voting member of the DEFUSE 3 Executive Committee (EC). Dr. [REDACTED] will be blinded to all outcome data during the study. Dr. [REDACTED] ~~will become unblinded~~ Upon database lock of the clinical database, Dr. [REDACTED] will receive unblinded data and will conduct the final analyses. Drs. [REDACTED] and [REDACTED] will be responsible for developing and writing the statistical analysis plan (SAP) prior to the initiation of the study, and SAP amendments, if any, during the study. The statistical team at MUSC, led by Dr. [REDACTED] will be unblinded throughout the study. The MUSC team will ~~implement the adaptive design algorithm developed and written by Dr. [REDACTED]~~ conduct and independently validate the interim analyses according to the SAP; generate Open and Closed Reports for the DSMB and interact with the DSMB in closed sessions; and collaborate with Dr. [REDACTED] on validation of final analyses. After database lock, the MUSC statistical team will create the public use datasets (PUDS) and submit them to the NINDS.

15. References

